10.7. Appendix 7: ECG Findings of Potential Clinical Concern

ECG Findings That May Qualify as AE

• Marked sinus bradycardia (rate <40 bpm) lasting minutes.• New PR interval prolongation >280 ms.• New prolongation of QTcF to >480 ms (absolute) or by ≥ 60 ms from baseline.• New-onset atrial flutter or fibrillation, with controlled ventricular response rate: ie, rate <120 bpm.• New-onset type I second-degree (Wenckebach) AV block of >30 seconds' duration.• Frequent PVCs, triplets, or short intervals (<30 seconds) of consecutive ventricular complexes.
ECG Findings That May Qualify as Serious AE

• QTcF prolongation >500 ms.• New ST-T changes suggestive of myocardial ischemia.• New onset left bundle branch block (QRS complex >120 ms).• New onset right bundle branch block (QRS complex >120 ms).• Symptomatic bradycardia.• Asystole:
• In awake, symptom-free participants in sinus rhythm, with documented periods of asystole ≥ 3.0 seconds or any escape rate <40 bpm, or with an escape rhythm that is below the AV node.• In awake, symptom-free participants with atrial fibrillation and bradycardia with 1 or more pauses of at least 5 seconds or longer.• Atrial flutter or fibrillation, with rapid ventricular response rate: rapid = rate >120 bpm.• Sustained supraventricular tachycardia (rate >120 bpm) ("sustained" = short duration with relevant symptoms or lasting >1 minute).• Ventricular rhythms >30 seconds' duration, including idioventricular rhythm (heart rate <40 bpm), accelerated idioventricular rhythm (HR >40 bpm to <100 bpm), and

monomorphic/polymorphic ventricular tachycardia (HR >100 bpm [such as torsades de pointes]).

- Type II second-degree (Mobitz II) AV block.
- Complete (third-degree) heart block.

ECG Findings That Qualify as SAE

- Change in pattern suggestive of new myocardial infarction.
- Sustained ventricular tachyarrhythmias (>30 seconds' duration).
- Second- or third-degree AV block requiring pacemaker placement.
- Asystolic pauses requiring pacemaker placement.
- Atrial flutter or fibrillation with rapid ventricular response requiring cardioversion.
- Ventricular fibrillation/flutter.
- At the discretion of the investigator, any arrhythmia classified as an adverse experience.

The enumerated list of major events of potential clinical concern are recommended as "alerts" or notifications from the core ECG laboratory to the investigator and Pfizer study team, and not to be considered as all-inclusive of what to be reported as AEs/SAEs.

10.8. Appendix 8: Country-Specific Requirements

See the individual [sub-study protocols](#) for any country-specific requirements.

10.9. Appendix 9: Alternative Measures During Public Emergencies

The alternative study measures described in this section are to be followed during public emergencies, including the COVID-19 pandemic. This appendix applies for the duration of the COVID-19 pandemic globally and will become effective for other public emergencies only upon written notification from Pfizer.

Use of these alternative study measures are expected to cease upon the return of business as usual circumstances (including the lifting of any quarantines and travel bans/advisories).

10.9.1. Eligibility

See the individual [sub-study protocols](#) for specific requirements.

10.9.2. Telehealth Visits

In the event that in-clinic study visits cannot be conducted, every effort should be made to follow up on the safety of study participants at scheduled visits per the Schedule of Activities or unscheduled visits. Telehealth visits may be used to continue to assess participant safety and collect data points. Telehealth includes the exchange of healthcare information and services via telecommunication technologies (eg, audio, video, video-conferencing software) remotely, allowing the participant (and possibly an accompanying informant) and the investigator to communicate on aspects of clinical care, including medical advice, reminders, education, and safety monitoring. The following assessments may be performed during a telehealth visit:

- Review and record study intervention(s), including compliance and missed doses.
- Review and record any AEs and SAEs since the last contact. Refer to Section 8.3.
- Review and record any new concomitant medications or changes in concomitant medications since the last contact.
- Review and record contraceptive method and results of pregnancy testing. Confirm that the participant is adhering to the contraception method(s) required in the protocol. Refer to Appendix 4 of each [sub-study protocol](#) for contraception and pregnancy testing.

Study participants must be reminded to promptly notify site staff about any change in their health status.

10.9.3. Alternative Facilities for Safety Assessments

10.9.3.1. Laboratory Testing

If a study participant is unable to visit the site for protocol-specified safety laboratory evaluations, testing may be conducted at a local laboratory if permitted by local regulations. The local laboratory may be a standalone institution or within a hospital. See the individual sub-study protocols for safety laboratory evaluations which may be performed at a local laboratory.

If a local laboratory is used, qualified study site personnel must order, receive, and review results. Site staff must collect the local laboratory reference ranges and certifications/accreditations for filing at the site. Laboratory test results are to be provided to the site staff as soon as possible. The local laboratory reports should be filed in the participant's source documents/medical records. Relevant data from the local laboratory report should be recorded on the CRF.

If a participant requiring pregnancy testing cannot visit a local laboratory for pregnancy testing, a home urine pregnancy testing kit with a sensitivity of at least 25 mIU/mL may be used by the participant to perform the test at home, if compliant with local regulatory requirements. The pregnancy test outcome should be documented in the participant's source documents/medical records and relevant data recorded on the CRF. Confirm that the participant is adhering to the contraception method(s) required in the protocol.

10.9.3.2. Imaging

If the participant is unable to visit the study site for imaging assessment(s), the participant may visit an alternative facility to have the imaging assessment(s) performed. Qualified study site personnel must order, receive, and review results.

10.9.3.3. Electrocardiograms

If the participant is unable to visit the study site for ECGs, the participant may visit an alternative facility to have the ECGs performed. Qualified study site personnel must order, receive, and review results.

10.9.4. Study Intervention

If the safety of a trial participant is at risk because they cannot complete required evaluations or adhere to critical mitigation steps, then discontinuing that participant from study intervention must be considered.

The following is recommended for the administration of study intervention for participants who have active confirmed (positive by regulatory authority-approved test) or presumed (test pending/clinical suspicion) SARS-CoV-2 infection:

[figure not shown]
- For symptomatic participants with active SARS-CoV-2 infection, study intervention should be delayed for at least 14 days from the start of symptoms. This delay is intended to allow the resolution of symptoms of SARS-CoV-2 infection.
- Prior to restarting treatment, the participant should be afebrile for 72 hours, and SARS-CoV-2-related symptoms should have recovered to Grade ≤ 1 for a minimum of 72 hours. Notify the study team when treatment is restarted.
- Continue to consider potential drug-drug interactions as described in the individual sub-study protocols for any concomitant medication administered for treatment of SARS-CoV-2 infection.

10.9.5. Adverse Events and Serious Adverse Events

If a participant has COVID-19 during the study, this should be reported as an AE or SAE and appropriate medical intervention provided. Temporary discontinuation of the study intervention may be medically appropriate until the participant has recovered from COVID-19.

It is recommended that the investigator discuss temporary or permanent discontinuation of study intervention with the medical monitor.

10.10. Appendix 10: Subcutaneous Injection Site Locations

Injection site locations include a maximum of 4 unique administration sites distributed across the 2 lower and the 2 upper abdominal quadrants (up to 1 injection location per quadrant).

Administer the required number of injections in the following order:

1. Lower left quadrant;
2. Lower right quadrant
3. Upper left quadrant
4. Upper right quadrant

Injections to the abdomen are preferred. If SC injections in the abdominal location are not possible, SC injections can be administered in a distributed manner in the thighs. SC injections in the upper extremities (eg, deltoid, upper and lower arm) are not permitted.

If more than 1 study intervention is administered SC, the 2 treatments should not be administered in the same quadrant whenever possible so that it will be easier to distinguish which drug caused any injection site reactions that may occur.

Track the participant's injection site(s) sequentially on this diagram with a red pen and mark the injection sites on the participant's abdomen according to your clinic's standard practice.

Record the location, time of each injection and any injection site reactions in the participant's source records and CRF. See Section 8.3 for AE reporting.

10.11. Appendix 11: IMWG Response Criteria for Multiple Myeloma

Participants must have measurable disease at enrollment (study entry) as defined by:

- Serum M protein ≥ 0.5 g/dL (5 g/L);
- Urine M protein ≥ 200 mg/24 hours;
- Serum FLC assay: involved FLC level ≥ 10 mg/dL (≥ 100 mg/L) AND abnormal serum immunoglobulin kappa to lambda FLC ratio (< 0.26 or > 1.65).

Whenever more than 1 parameter is used to assess response, the overall assigned level of response is determined by the lowest level of response.

All response assessments will be entered on the CRF.

All response categories require 2 consecutive assessments made any time before starting new therapy. To confirm response or PD, 2 discrete samples are required, and testing cannot be based upon the splitting of a single sample.

Response ^a	Modified IMWG Criteria
Sustained MRD-negative	
 • CR as defined below plus: • MRD negativity in the marrow (NGF or NGS, or both) and by imaging as defined below, confirmed minimum of 1 year apart. Subsequent evaluations can be used to further specify the duration of negativity (eg, MRD-negative at 5 years)
Flow MRD-negative	
 • CR as defined below plus: • Absence of phenotypically aberrant clonal plasma cells by NGF on BMA using the EuroFlow standard operation procedure for MRD detection in MM (or validated equivalent method) with a minimum sensitivity of 1 in 10^5 nucleated cells or higher
Sequencing MRD-negative	
 • CR as defined below plus: • Absence of clonal plasma cells by NGS on BMA in which presence of a clone is defined as less than 2 identical sequencing reads obtained after DNA sequencing of BMA using the LymphoSIGHT platform (or validated equivalent method) with a minimum sensitivity of 1 in 10^5 nucleated cells or higher
Imaging plus MRD-negative	
 • CR as defined below plus: • MRD negativity as defined by NGF or NGS plus disappearance of every area of increased tracer uptake found at baseline or a preceding PET/CT or decrease to less mediastinal blood pool SUV or decrease to less than that of surrounding normal tissue
Stringent Complete Response (sCR)	
 • CR as defined below plus: 
 – Normal serum FLC ratio and absence of clonal cells in BMA/BMB by immunohistochemistry, immunofluorescence (eg, flow cytometry).^{b,c} – If the only measurable disease is by serum FLC levels, sCR is defined as normal serum FLC ratio of 0.26 to 1.65 plus absence of clonal cells in BMA/BMB by immunohistochemistry, immunofluorescence (eg, flow cytometry).^{b,c}

090177e19f0abbfaApproved\Approved On: 31-Oct-2023 20:35 (GMT)

Response ^a	Modified IMWG Criteria
Complete Response (CR)	
 Negative immunofixation on serum and urine, disappearance of any soft tissue plasmacytomas and <5% plasma cells in BMA.^{b,d} If the only measurable disease is by serum FLC levels, CR is defined as normal serum FLC ratio of 0.26 to 1.65, plus criteria listed above.^{b,d}
Very Good Partial Response (VGPR)	
 Serum and urine M-protein detectable by immunofixation but not on electrophoresis. OR ≥90% reduction in serum M-protein plus urine M-protein level <100 mg/24 h. If the only measurable disease is by serum FLC levels, VGPR is defined as a ≥90% decrease in the difference between involved and uninvolved serum FLC levels. In addition to these criteria, if present at baseline, a >90% reduction compared with baseline in the size (SPD) of soft tissue plasmacytomas^d
Partial Response (PR)	
 ≥ 50% reduction of serum M-protein and reduction in 24 hours urinary M-protein by ≥90% or to <200 mg/24 h. If the serum and urine M-protein are unmeasurable, a ≥50% decrease in the difference between involved and uninvolved serum FLC levels is required in place of the M-protein criteria. In addition to these criteria, if present at baseline, a ≥50% reduction in the size (SPD) of soft tissue plasmacytomas is also required.^d
Minimal Response (MR)	
 ≥25% but ≤49% reduction of serum M-protein and reduction in 24-h urine M-protein by 50%–89%. In addition to these, if present at baseline, a ≥50% reduction in the size (SPD) of soft tissue plasmacytomas is also required.^d
No Change/Stable Disease (SD)	
 Not meeting criteria for sCR, CR, VGPR, PR, MR or PD.
Progressive Disease (PD) ^{b,e,f}	
Any 1 or more of the following criteria:
 
 Increase of ≥25% from lowest confirmed response value in any 1 or more of the following:^{e,f} Serum M-component (the absolute increase must be ≥0.5 g/dL); Serum M-protein increase ≥1 g/dL, if the lowest M component was ≥5 g/dL; Urine M-protein (the absolute increase must be ≥200 mg/24 h). In participants without measurable serum and urine M-protein levels, the difference between involved and uninvolved serum FLC levels (absolute increase must be >10 mg/dL); In patients without measurable serum and urine M-protein levels and without measurable involved serum FLC levels, bone marrow plasma-cell percentage irrespective of baseline status (absolute increase must be ≥10%). Appearance of a new lesion(s), ≥50% increase from nadir in SPD of >1 lesion, or ≥50% increase in the longest diameter of a previous lesion >1 cm in short axis.^d ≥50% increase in circulating plasma cells (minimum of 200 cells per μL) if this is the only measure of disease

a All response categories require 2 consecutive assessments made any time before starting new therapy. Each category (except stable disease) will be considered unconfirmed until confirmatory test is performed. All categories (stable disease or better) require no known evidence of PD, new bone lesions or EMD plasmacytomas if imaging studies were performed; imaging studies are not required to satisfy these response requirements except for requirement of FDG PET to confirm imaging plus MRD-negative.

Response ^a	Modified IMWG Criteria
b	Bone marrow assessments do not need to be confirmed. Careful attention should be given to new positive immunofixation results appearing in participants who have achieved a CR, when the isotype is different. This often represents oligoclonal immune reconstitution and should not be confused with relapse; these bands typically disappear over time.
c	Presence/absence of clonal cells is based upon the κ/λ ratio. An abnormal κ/λ ratio by IHC or immunofluorescence requires a minimum of 100 plasma cells for analysis. An abnormal ratio reflecting presence of an abnormal clone is κ/λ of $>4:1$ or $<1:2$.
d	Plasmacytoma measurements should be taken from the CT portion of the PET/CT, or dedicated CT scans where applicable. Measurement of tumor size will be determined by the SPD.
e	PD confirmation requires two consecutive assessments made at any time prior to the institution of any new anticancer therapy. If alternate therapy is started before confirming PD, any additional testing during subsequent therapy can be used to confirm PD. Participants will be considered to have PD if they meet the criteria for progression by a variable that was not considered measurable at baseline; however, for participants who had a measurable serum or urine M-protein (M-spike) at baseline, PD cannot be defined by increases in serum FLC alone.
f	For PD, serum M-component increases of ≥ 1 mg/dL are sufficient to define relapse if starting M-component is ≥ 5 g/dL.

ADDITIONAL NOTES:

- If participants do not have measurable disease at baseline they can only be assessed for at least a CR or PD.
- Serum FLC levels should only be used for response assessment when both the serum and urine M-component levels are deemed not measurable (including at suspected CR).
- In cases where SPEP is found to be unreliable (eg, IgA, IgD myelomas) for M-protein assessment, quantitative immunoglobulin measurements are preferred for disease assessment; the same percentage changes apply as for serum M-protein. If used, quantitative immunoglobulin assessment must be used exclusively for a participant (ie, quantitative immunoglobulin and SPEP cannot be used interchangeably for disease assessment of the same participant).

Source: Adapted from (Kumar et al, 2016)

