7.1. Discontinuation of Study Intervention

It may be necessary for a participant to permanently discontinue study intervention. Reasons for permanent discontinuation of study intervention may include the following:

- Objective disease progression;
- Lack of efficacy (eg, increase of disease burden not qualifying as PD according to IMWG criteria)
- Global deterioration of health status requiring discontinuation;
- Unacceptable toxicity;
- Pregnancy or breastfeeding;
- Medication error without associated adverse event
- Significant protocol violation;
- Lost to follow-up;
- Participant refused further treatment;
- Withdrawal by participant;
- Investigator decision;
- Study completed;
- Study terminated by sponsor;
- Death.

Note that discontinuation of study intervention does not represent withdrawal from the study. If study intervention is permanently discontinued, the participant will remain in the study to be evaluated for safety, disease assessments, subsequent anti-cancer therapies and survival. Refer to each [sub-study protocol](#) SoA for data to be collected at the time of discontinuation of study intervention and follow-up for any further evaluations that need to be completed.

In the event of discontinuation of study intervention, it must be documented on the appropriate CRF/in the medical records whether the participant is discontinuing further receipt of study intervention or also from study procedures, post-treatment study follow-up, and/or future collection of additional information.

7.1.1. Follow-Up Visits (28/90 Days):

7.1.1.1. 28-35 Days Post-Dose

At least 28 calendar days, and no more than 35 calendar days after discontinuation of study intervention, participants will return to clinic for a safety follow-up visit, including review of concomitant treatments, vital signs, and assessment for resolution of any treatment-related AEs (refer to each [sub-study protocol](#) SoA for all activities).

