8.1. Efficacy Assessments

Disease response will be assessed according to IMWG response criteria ([Appendix 11](#)). All response categories (except stable disease) require 2 consecutive assessments (confirmation).

Disease assessments should continue up through the End of Treatment visit if the End of Treatment reason is PD. For participants that discontinue study intervention without disease progression and remain in follow-up, disease assessments should be conducted every 4 weeks until PD, withdrawal of consent, lost to follow-up, death, or defined end of study (whichever occurs first).

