- Population-level summary measure: ORR defined as the proportion of participants in the analysis population with an objective response. The median and its corresponding 2-sided 90% credible interval of ORR in the analysis population based on the posterior distribution will be calculated.

Additionally, the observed point estimate of ORR will be calculated along with the 2-sided 90% CIs using the Clopper-Pearson method (exact CI for a binomial proportion).

The frequency (number and percentage) of participants with BOR by investigator in each response category will be summarized: sCR; CR; VGPR; PR; MR; SD; PD; Not evaluable (NE)/unknown.

In addition, the following response categories will be calculated along with corresponding 2-sided exact 95% CIs using the Clopper-Pearson method:

- VGPR or better (sCR + CR + VGPR);
- Clinical benefit (sCR + CR + VGPR + PR + MR).

BOR will be assessed programmatically based on reported timepoint responses by investigator recorded at evaluation time points from the date of first dose until confirmed disease progression, death or start of new anticancer therapy using IMWG response criteria. BOR needs to be confirmed according to IMWG response criteria (Table 4). If a participant meets multiple criteria in determining confirmed BOR, the order of criteria in this table will be used to define the hierarchy. Twenty-eight days is the scheduled gap between the disease assessments after cycle 1. If a confirmation is to be done on the same day, a different sample is required for confirmation. A confirmatory response assessment may be performed >28 days following the initial response assessment, allowing for a maximum of 1 intervening missing or not evaluable assessment.

For participants with EMD at baseline, MR or better (for those with target plasmacytomas) and CR or better (for those with non-target non-bone EMD only) cannot be confirmed until a post-baseline EMD assessment is performed.

The rules for PD confirmation apply to both confirmed PD as BOR and confirmed PD after BOR (for time-to-event endpoint analyses), and the PD date is the date of the initial PD assessment.

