### 6.2.2. Progression-free Survival

PFS is defined as the time from the date of first dose until confirmed PD per IMWG criteria as determined by investigator or death due to any cause, whichever occurs first. The rules for PD confirmation are described in [Table 4](#).

PFS will be calculated as follows:

$$\text{PFS (months)} = [\text{date of event or censoring} - \text{date of first dose} + 1] / 30.4375.$$

PFS will be censored as follows:

- For participants who do not have an event (confirmed PD per IMWG criteria or death due to any cause), censoring will occur on the date of the last adequate disease assessment;
- For participants who start a new anticancer therapy (as defined in [Section 5.2.6 in the master SAP](#)) prior to an event, censoring will occur on the date of the last adequate disease assessment before the new anticancer therapy;
- For participants with an event after a gap of 2 or more missing disease assessments, censoring will occur on the date of the last adequate disease assessment before the gap;
- Participants who do not have an adequate post-baseline disease assessment will be censored on the date of first dose of study intervention unless death occurs on or before the time of the second planned disease assessment (i.e.,  $\leq 70$  days after the date of first dose) in which case the death will be considered an event.

The censoring and event date options to be considered for the PFS analysis are presented in Table 5. Adequate post-baseline disease assessment is defined in [Section 5.2.10 in the master SAP](#).

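### Footnote f of Protocol Appendix 11 gives the progression threshold at high M-component as 1 mg/dL; the PD row it annotates says 1 g/dL

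*Protocol*

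**What the plan says.** Protocol 8.1 makes Appendix 11 the working definition: "Disease response will be assessed according to IMWG response criteria".

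In Appendix 11 (Section 10.11) the PD row offers several routes to progression. Three pieces of text in that row bear on serum M-component:

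- a relative rise: "25% from lowest confirmed response value in any 1 or more of the following";
- a general absolute minimum: "Serum M-component (the absolute increase must be ≥0.5 g/dL";
- a rule for high values: "Serum M-protein increase ≥1 g/dL, if the lowest M component was ≥5 g/dL".

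Footnote f is marked on the PD heading and again on the lead-in with the relative rise. It covers the same high-value group: "For PD, serum M-component increases of ≥ 1 mg/dL are sufficient to define relapse if starting M-component is ≥ 5 g/dL".

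On the analysis side, the sub-study A SAP (Section 6.1.2) states that "BOR will be assessed programmatically based on reported timepoint responses by investigator", and its Section 6.2.2 states that "PFS is defined as the time from the date of first dose until confirmed PD per IMWG criteria as determined by investigator". The sub-study B SAP and the master SAP also take progression from the investigator.

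**The concern.** Two thresholds are printed for one situation, in different units. Both are current text, and neither is redacted or part of the amendment history. Nothing else in the master protocol or the SAPs restates or corrects the value. The sub-study protocols are not among the documents and could not be checked.

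A rise of 1 mg/dL at 5 g/dL is far below what serial electrophoresis can distinguish from noise. An investigator who applied the footnote as printed could call PD, and confirm it on a second sample, in a participant whose disease had not changed. The SAPs use that call as reported and describe no check of it against the M-protein values. At stake are a false PFS event, an early close of the window in which best response is assessed, and possibly the end of treatment. Protocol 7.1 says "Reasons for permanent discontinuation of study intervention may include the following", and objective progression is the first item on that list.

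**Working it through.** No sample size, power or error rate depends on this point. The check is a comparison of texts with a unit conversion.

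**Inputs (all Protocol Appendix 11)**

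- Footnote f: rise of at least 1 mg/dL = 0.001 g/dL, M-component at least 5 g/dL.
- PD row, high-value item: rise of at least 1 g/dL, lowest M-component at least 5 g/dL.
- PD row, general minimum: rise of at least 0.5 g/dL.
- PD row, relative rise: at least 25%.

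**Comparison**

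- Row against footnote: 1 / 0.001 = 1000.
- General minimum against footnote: 0.5 / 0.001 = 500.
- Footnote as a share of 5 g/dL: 0.001 / 5 = 0.02%.
- Row item as a share of 5 g/dL: 1 / 5 = 20%.
- Relative rule at 5 g/dL: 0.25 × 5 = 1.25 g/dL.

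With g/dL in the footnote, it matches the row. With mg/dL, participants with the highest M-component would need the smallest rise of all, 500 times less than participants below 5 g/dL. The footnote is therefore the text in error.

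**Would confirmation stop it?** Suppose a stable participant is judged by the literal footnote, with the first reading as reference. Assume a true value of 5.5 g/dL and a measurement CV of 1% to 5%; the documents give neither figure. Even at 1%, the error SD is 0.01 × 5.5 = 0.055 g/dL, or 55 mg/dL, so a 1 mg/dL margin is negligible. The next two samples then both qualify roughly whenever the first of three exchangeable readings is the lowest, which has probability 1/3. Simulation at CVs of 1%, 3% and 5% gives:

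- unrounded: 0.328, 0.331, 0.309;
- reported to 0.1 g/dL: 0.144, 0.254, 0.269.

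Under the same assumptions at 1 g/dL, the chance of any two consecutive qualifying samples in six assessments is at most 0.0006. If M-component falls 10% per assessment, the chance that the next two samples both meet the 1 mg/dL rule is at most 0.0001.

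So confirmation is a weak safeguard if the footnote is followed, and participants who are clearly responding are not exposed. These figures describe the rule. They do not say how often it would be used.

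**The case against.** The strongest reply is that this is a visible slip with its correction printed beside it. A reader reaches footnote f through a row that states 1 g/dL for this group and 0.5 g/dL in general. A 0.02% rise is implausible as relapse, and most myeloma investigators would see that. PD on M-component also needs two consecutive assessments. PFS in sub-study A is a secondary, single-arm, descriptive endpoint. Protocol 7.1 lists progression as a possible reason for stopping, so a stop is not automatic. All of this stands, and it is why the point is minor.

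Three stronger readings might be inferred, and the documents do not support them.

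- **That the footnote is the clause that makes the rule work.** The argument is that the 1 g/dL item sits under the 25% lead-in, where 1.25 g/dL is already needed, so only the footnote permits a smaller rise. That depends on the nesting of a table that was flattened when its text was extracted. The item is worded as a complete criterion, while its neighbours name an analyte with a bracketed minimum, and the row heading allows any one criterion to suffice. Read that way, it decides cases without the footnote.
- **That a number of false PFS events can be expected.** Such a count needs the number of participants stable at 5 g/dL or more, their true values, the assay CV, and the chance that an investigator prefers the footnote to the row. The documents give none of these.
- **That ORR or DOR is biased.** ORR changes only if a participant wrongly called progressive would have responded later. On the row's reference value, a partial responder whose lowest value is still 5 g/dL would need a baseline of 5 / 0.5 = 10 g/dL, so no DOR effect is claimed.

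**Conclusion.** The inconsistency is real: footnote f carries the wrong unit and is 1000 times too small against the row it annotates. It matters in kind because it is a decision threshold in the operative criteria, and investigator-reported PD passes into best response and PFS with no described check against the laboratory values.

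Its likely size is small. Harm requires that an investigator follow the footnote over the row, that the participant have an M-component of at least 5 g/dL without a clear fall, and that the second sample also meet the wrong threshold. The probability of the first and the number of such participants are unknown, so no expected effect on any endpoint is given. This is a minor internal inconsistency in the protocol. It is not a flaw in the choice of analysis.

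**What to change.** At the next protocol amendment, change the rise in footnote f to ≥1 g/dL. In the same sentence, change the reference from the starting to the lowest M-component, as in the PD row; otherwise it could be taken to mean baseline.

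Before analysis, list and query every PD reported on serum M-component alone where the reference value was at least 5 g/dL and the rise was under 1 g/dL. This finds any case in which the printed footnote was followed.

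The cost is one unit, one word and one query listing. No new data collection and no SAP change are needed.
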